(e.g. glycemic variability); 2) the molecular and metabolic mechanisms by which unawareness leads to the suppression of CNS activity in the context of hypoglycemia; and 3) whether hypoglycemia avoidance using CGM restores CNS activation and metabolism toward normal levels and offers a therapeutic approach to more effectively combat neurocognitive dysfunction associated with intensive treatment of T1DM patients.

4. **Research Plan:** Summarize the study design and research procedures using non-technical language that can be readily understood by someone outside the discipline. **Be sure to distinguish between standard of care vs. research procedures when applicable, and include any flowcharts of visits specifying their individual times and lengths.** Describe the setting in which the research will take place.

Aim 1: Studies will be conducted in non-diabetic controls (N=25) and 2 groups of subjects with T1DM without significant complications: (1) hypoglycemia unaware (T1DM-UA) (N=40) and (2) hypoglycemia aware (T1DM-A) (N=25).

1. Screening visit: Volunteers will be screened at the Yale New Haven Hospital (YNHH) Hospital Research Unit (HRU) or the Yale Center for Clinical Investigation (YCCI) Church Street Research Unit (CSRU) with a medical history, physical exam, and EKG. Fasting blood work will be collected for A1C, ALT, TSH, electrolytes, renal function, CBC, and C-peptide. A urine pregnancy test will be performed on all women of childbearing potential, and women who are pregnant will be excluded.

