 - b. Fear of Hypo : Measures worry about hypo episodes and behavior to avoid them, 2 sub scores available.
 - c. Hypo AQ : Hypo Awareness Questionnaire measures awareness, symptom level, and frequency of hypo episodes
 - d. Hypo Confidence : measures confidence in managing hypo episodes
 - e. DTSQ: Diabetes Treatment Satisfaction Questionnaire, measures satisfaction, hyper frequency, and hypo frequency.
 - f. DQOL: Diabetes Quality of Life: four sub scores (satisfaction, impact, worry: diabetes, worry: social)
 - g. BDI-II : Beck Depression Inventory: measures depressive symptoms
 - h. PSS: Perceived Stress score: measures how "unpredictable, uncontrollable, and overloaded respondents find their lives"
 - i. STAI: State Trait Anxiety Inventory: measure of anxiety symptoms as well as generalized anxiety
 - j. BIS/BAS: Behavioral avoidance/inhibition scales:
 - k. PANAS: Positive Affect, Negative Affect Score: Measures Affect
 - l. SF/RAND: short form quality of life questionnaire: designed to be general.

5. Genetic Testing N/A

6. **Subject Population:** Provide a detailed description of the types of human subjects who will be recruited into this study.

25 healthy control subjects, ages \geq 18 years, BMI \geq 18.0

65 subjects with T1DM, ages \geq 18 years, BMI \geq 18.0

7. **Subject classification:** Check off all classifications of subjects that will be specifically recruited for enrollment in the research project. Will subjects who may require additional safeguards or other considerations be enrolled in the study? If so, identify the population of subjects requiring special safeguards and provide a justification for their involvement.

 Children	 Healthy	 Fetal material, placenta, or dead fetus
 Non-English Speaking	 Prisoners	 Economically disadvantaged persons
 Decisionally Impaired	 Employees	 Pregnant women and/or fetuses
 Yale Students	 Females of childbearing potential	

NOTE: Is this research proposal designed to enroll children who are wards of the state as potential subjects?

Yes No

8. **Inclusion/Exclusion Criteria:** What are the criteria used to determine subject inclusion or exclusion?

Inclusion Criteria:

- Ages \geq 18 years
- Healthy, non-diabetic control or T1DM

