Data analysis will be conducted in collaboration with [name] at the Yale Center for Analytic Sciences. For Aim 1, we will require 25 T1DM aware and 25 healthy controls to provide 80% power to detect differences of 0.013 between them and the T1DM-Unaware subjects at the Bonferroni corrected 0.017 significance level. This sample size will also provide 80% power at the 0.01 level of significance to detect a difference of 0.22 for average brain glucose for Aim 2. We will enroll 27 aware and 27 healthy controls to accommodate a potential

5% inadequate scan rate. The T1DM Unaware group sample size (n=40) was first determined to provide sufficient power for Aim 3. T1DM Aware and healthy control sample sizes were then estimated based on power for aims 1 and 2. Our preliminary data shows differences in the co-primary outcome of average brain glucose between those with a low glucose variability index and those with a high glucose variability index of 0.455 (SD=0.26). We've also observed a difference of 0.013 (SD=0.016) in our other co-primary outcome change in brain activity from hypoglycemia to euglycemia in the striatum between T1DM Aware and Unaware. Thus, for Aim 3 a sample size of 20 T1DM Unaware subjects per arm will provide 80% power to detect a difference of 0.22 in brain glucose and 0.013 in change in brain activity. We will enroll 65 Unaware for Aim 3 in order to accommodate a potential 10% dropout rate.

Aim 1 Analysis: Comparison of brain activity between groups will be performed using a repeated measures mixed model. The outcome will be brain activity in our primary region of interest, the caudate region of the striatum. Fixed factors for group (unaware, aware, HC), glucose category (eugly, mild hypo, moderate hypo) and their interaction will be included. Linear contrasts comparing changes in brain activation from euglycemia to moderate hypo between groups will be estimated and evaluated at the 0.017 Bonferroni corrected significance level. Secondary analyses will examine other promising ROIs (hypothalamus and prefrontal cortex). Similar analyses will be done to assess group differences in resting state connectivity and hormones.

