- a) Maintains appropriate records, including receipt of shipment, inventory at the site, dispensation or use by each participant, and final disposition and/or the return of the investigational device (or other disposal if applicable): Electronic records (shipment receipts, inventory, participant use, return of device) will be stored in the study folder on the secured server on a password protected computer or laptop, which is kept in the PI's locked office. Any paper records will be scanned and stored in the file as well.
- b) Documents pertinent information assigned to the investigational device (e.g., date, quantity, batch or serial number, expiration date if applicable, and unique code number): Pertinent information assigned to the investigational device will be stored in an electronic file in the study folder on the secured server on a password protected computer or laptop, which is kept in the PI's locked office.

- c) Stores the investigational device according to the manufacturer's recommendations with respect to temperature, humidity, lighting, and other environmental considerations: Per the manufacturer's recommendations, the sensor kit will be stored in a location between 39-77 degrees Fahrenheit and between 10-90% non-condensing humidity. There are no other environmental considerations.
- d) Ensures that the device is stored in a secure area with limited access in accordance with applicable regulatory requirements: The sensor kit will be stored in the PI's locked office in a locked cabinet.
- e) Distributes the investigational device to subjects enrolled in the IRB-approved protocol: The device will be provided to subjects enrolled in this IRB-approved protocol after consent has been obtained and a study clinician has explained how to use the device and has determined that the subject understands how to use the device. Sufficient time will be provided in order for the subject to ask any questions they may have about the device and feel confident in using the device. The participants will be given one of the study physician or nurse practitioner's cell phone number to contact for any questions, concerns or problems.

SECTION III: RECRUITMENT/CONSENT AND ASSENT PROCEDURES

1. Targeted Enrollment: Give the number of subjects:

- a. Targeted for enrollment at Yale for this protocol: 150
- b. If this is a multi-site study, give the total number of subjects targeted across all sites: N/A

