- "You are receiving this notification because you may qualify and be interested in a study looking at mechanisms for restoration of hypoglycemia awareness. The Yale New Haven Health electronic health record system has searched medical conditions to find people who may be good matches for research studies. No one has looked at your record and no information has been shared with any research doctor or research team member. Just because you received this message does not mean that you are in a research study or that you have to decide to be in this or any study. You may be interested and eligible to participate in a research study conducted by Yale University investigators to better understand diabetes.

To opt-out of research, including opting out of receiving future messages about research studies, please email [contact] or call [name] and select option #3.

Title of study: Mechanisms for restoration of hypoglycemia awareness

Principal Investigator: [name], MD

Study Coordinator: [name]

[contact]

The message/mailing to potential study participants will also include the following information, regardless of who sends it:

- "You are receiving this notification because you may qualify and be interested in a study looking at mechanisms for restoration of hypoglycemia awareness. Approximately 65 subjects will be enrolled in this study.

Description of Study:

Aim 1: Determine the impact of frequent hypoglycemia and hypoglycemia unawareness on brain responses to visual food cues as well as brain functional connectivity in T1DM patients.

Aim 2: Assess the Impact of antecedent bouts of hypoglycemia on brain glucose transport/metabolism during hyperglycemia in T1DM Unaware, T1DM Aware as well as healthy controls using 1H, 13C magnetic resonance spectroscopy (MRS).

Aim 3: Determine if reducing hypoglycemia and glycemic variability using CGM reverses altered brain glucose transport/metabolism and functional connectivity in hypoglycemia unaware T1DM patients.

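### Section 13 enrols 27 Aware and 27 controls to secure 25 usable scans each, but Sections 4 and 6 give 25 and 25; the Unaware number and the study total are also unreconciled, with a modest effect on Aim 1 power

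*Combined protocol and SAP*

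**What the plan says.** **Section I.13 (Statistical Considerations).** For Aim 1, "we will require 25 T1DM aware and 25 healthy controls to provide 80% power" against the Unaware group at the "Bonferroni corrected 0.017 significance level". The planning values come from preliminary data, which "observed a difference of 0.013 (SD=0.016) in our other co-primary outcome change in brain activity". To cover a 5% rate of inadequate scans the section adds: "We will enroll 27 aware and 27 healthy controls to accommodate a potential". So 25 is the number of usable scans and 27 is the number to enrol. The same paragraph sets the Unaware group at 40, chosen for Aim 3, and then says 65 Unaware will be enrolled for Aim 3 to absorb 10% dropout.

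**Section I.4 (Research Plan).** "Studies will be conducted in non-diabetic controls (N=25) and 2 groups of subjects with T1DM", namely 40 Unaware and 25 Aware. Aim 3 then assigns 40 Unaware subjects.

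**Section I.6 (Subject Population).** The item asks who will be recruited. The answer is "25 healthy control subjects, ages" 18 or over, plus 65 subjects with T1DM.

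**Section III.1 (Targeted Enrollment).** "Targeted for enrollment at Yale for this protocol: 150".

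**Section III.3 (Recruitment Procedures, message text).** "Approximately 65 subjects will be enrolled in this study".

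**The concern.** The allowance for failed scans is worked out in the statistical section but does not reach the sections that describe the study groups and who will be recruited. Staff who recruit to Sections I.4 and I.6 would stop at 25 per group, and any failed scan would then take a group below the protocol's own requirement. The Unaware subjects have the same scans, yet the 5% allowance is applied only to the Aware and control groups.

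The Unaware number matters more for power than 25 against 27, and Section I.13 gives it two values, 40 and 65. A reader cannot tell whether Aim 1 is adequately powered without knowing which applies. The totals offer no way to settle it, because no two of them agree. One of them is in a message sent to prospective participants.

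**Working it through.** **Inputs.** Difference 0.013, SD 0.016, alpha 0.017, 25 usable scans per comparison group, 40 Unaware and a 5% scan loss, all from Section I.13. Sidedness is not stated for Aim 1; two-sided is assumed.

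**Formula.** Standardised difference = 0.013/0.016 = 0.8125. Noncentrality = 0.8125 / √(1/n₁ + 1/n₂). Normal-approximation power = Φ(noncentrality − 2.387), where 2.387 is the two-sided 0.017 critical value. The t figure uses the noncentral t with n₁ + n₂ − 2 degrees of freedom.

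**The plan's figure.** At 25 vs 40 the noncentrality is 0.8125/√(1/25 + 1/40) = 3.187. Power is Φ(0.800) = 78.8% (normal) or 76.7% (t). The stated 80% is reproduced to within about a point by the normal approximation, but not by the t-test.

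**Inflation.** 25/0.95 = 26.3, so 27 is right. Expected usable scans are 27 × 0.95 = 25.65 (about 26) and 25 × 0.95 = 23.75 (about 24). For 40 Unaware, 40 × 0.95 = 38.

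**Chance of at least 25 usable scans in a group** (binomial, 5% loss per scan): with 25 enrolled, 0.95²⁵ = 28%; with 27 enrolled, 85%.

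**Aim 1 power, two-sided 0.017**

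| Usable scans (Aware or control vs Unaware) | Situation | t | Normal |
|---|---|---|---|
| 25 vs 40 | no loss | 76.7% | 78.8% |
| 24 vs 40 | 25 enrolled, loss in that group only | 75.4% | 77.6% |
| 26 vs 40 | 27 enrolled, loss in that group only | 77.8% | 79.9% |
| 24 vs 38 | 25 enrolled, loss in all groups | 74.4% | 76.7% |
| 26 vs 38 | 27 enrolled, loss in all groups | 76.8% | 79.0% |

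**Where the gap to 80% comes from.** At 24 vs 38 the gap is 5.6 points (t) or 3.3 (normal).
- Already present at 25 vs 40: 80 − 76.7 = 3.3 (t), 80 − 78.8 = 1.2 (normal).
- Going from 25 to 24 comparison scans: 76.7 − 75.4 = 1.3 (t), 78.8 − 77.6 = 1.2 (normal).
- Going from 40 to 38 Unaware scans: 75.4 − 74.4 = 1.0 (t), 77.6 − 76.7 = 0.9 (normal).

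Enrolling 25 rather than 27, with 38 usable Unaware in both cases, costs 76.8 − 74.4 = 2.4 points (t) or 79.0 − 76.7 = 2.3 (normal).

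**The Unaware number.** Allowing for 10% dropout, 40/0.9 = 44.4, so 45, not 65. If 65 were enrolled, 10% dropout leaves 65 × 0.9 = 58.5, about 58. Then 24 vs 58 has noncentrality 0.8125/√(1/24 + 1/58) = 3.348, and power is 82% (t) or 83% (normal).

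**Totals.** Section I.6: 25 + 65 = 90; the sum is not printed. Section I.4: 25 + 25 + 40 = 90. Section I.13: 27 + 27 + 40 = 94, or 27 + 27 + 65 = 119. Section III.1: 150. Message: about 65, which equals the T1DM subtotal 40 + 25.

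**The case against.** A reader might infer that the 25-versus-27 discrepancy is why Aim 1 falls short of 80%. The documents do not support that. With no scan loss at all, 25 vs 40 already gives 76.7% (t) or 78.8% (normal). Carrying 27/27 through every section still leaves 77-79% once all groups lose 5%. The effect of the discrepancy, about 2 points, is no larger than the spread between the t and normal calculations, and a one-sided test at 0.017 would give 83.4% (t) even at 24 vs 40. This objection stands, and it limits the point to a small loss.

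It can also be said that nothing makes Sections I.4 and I.6 override Section I.13, which is the only place with an explicit inflated target, and that N=25 in Section I.4 may simply mean evaluable subjects. That reading is possible for Section I.4. It is hard to sustain for Section I.6, whose item asks about subjects to be recruited.

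On the totals, a reader might infer that the message's figure of 65 matches nothing else. It does match the T1DM subtotal, and the search that triggers the message uses type 1 diabetes codes. But the sentence is worded for the whole study, and the description that follows includes healthy controls under Aim 2. The 150 may count screen failures; the protocol does not say so.

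**Conclusion.** The inconsistency is real and sits in the current text. Aware and control enrolment is 27/27 in one section and 25/25 in two others, the Unaware number is both 40 and 65, and totals of 90 (derived), 150 and about 65 are left unreconciled.

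For Aim 1, with 40 Unaware enrolled and 5% scan loss in all groups, power is about 74-77% under 25/25 and about 77-79% under 27/27. The missing allowance accounts for about 2 points. The rest of the gap to 80% comes from the calculation itself and from giving the Unaware group no scan loss. It cannot be concluded that Aim 1 is underpowered whatever happens: if 65 Unaware are enrolled, power is above 80%.

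These figures assume a two-sided test, a common SD of 0.016, a simple two-group comparison in place of the planned mixed-model contrast, and scan losses at exactly the expected rate. The plainest measure of what is lost is the 28% against 85% chance that a group reaches its required 25 usable scans.

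**What to change.** 1. Use one enrolment number per group in Sections I.4, I.6 and I.13. Section I.13 already states 27 Aware and 27 controls; carry these over, or state that 25/25 is intended and drop the allowance.
2. Replace 40 and 65 with a single Unaware enrolment figure and show its derivation. If 40 completers are needed and dropout is 10%, the arithmetic gives 45.
3. Restate Aim 1 power on expected usable scans in all three groups, naming the test and its sidedness. With 40 Unaware enrolled this is about 77-79% for 27/27, or about 74-77% if 25/25 is kept. Recompute if another Unaware number is chosen.
4. Give one total in Section I.6, Section III.1 and the recruitment message. Say whether 150 counts screen failures and whether 65 means T1DM subjects only.

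The cost is wording in these sections and in the message, two more Aware subjects and two more controls than Sections I.4 and I.6 now list if 27/27 is adopted, and a power figure slightly below 80% if the Unaware number is 40.

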1. Group Assignment: 40 T1DM-UA subjects will be assigned to use a Dexcom G6 continuous monitoring system for 8 to 12 weeks, until they reach stable glycemic variability measured by coefficient of variation (CV) Additional training sessions will be conducted as needed to ensure familiarity and comfort with system operation.
2. Continuous glucose monitoring (CGM): Dexcom G6 continuous glucose monitoring system (DexcomG6 Pro System) is a real time continuous glucose monitoring device indicated for the management of diabetes in persons age 2 years and older. Is factory calibrated so there is no need for calibrations. It replaces fingerstick blood glucose testing for diabetes treatment decisions. The real-time Dexcom G6 System provides glucose trends, several sequential readings over time and glucose excursions facilitating care plan adjustments. This device may also be used as a retrospective glucose-recording device indicated for assessing glycemic variability.

The CGM consists of a sensor that measures glucose levels from the interstitial tissue. The CGM includes an applicator with a build-in sensor, which is packaged in a sterile unopened package. The sensor has a plastic wire-like tip that is placed under the skin and continuously measures the glucose level. The sensor can be worn for up to 10 days. It also comes with a transmitter, which connects to the sensor wire and sends real-time readings wirelessly to a receiver.

3. Follow-up visits: Subjects will be instructed to share data remotely to the study team through Dexcom Clarity, a continuous glucose monitor management application run by Dexcom. A member of the study team (physician and/or advanced practice register nurse) will review the information on a weekly basis and will make changes to their diabetes management as needed. Study participants will have in-person check-in visits for history, exam, and review of any potential adverse clinical or device-related events, if needed.

A study team member will communicate directly with the participants and participant's health care providers as they join the study and throughout the study, and will inform them about relevant clinical findings on the CGM including time spent in hyperglycemia and new increase or extended periods of hypoglycemia

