4. Repeat brain MRS and fMRI scans: At 12 weeks, all subjects will repeat fMRI and MRS analyses of brain glucose transport/metabolism under hypo- and hyperglycemia exactly as described in Aims 1 and 2. At 12 weeks, the subjects in Group 2 will repeat fMRI and MRS analyses of brain glucose transport/metabolism under hypo- and hyperglycemia exactly as described in Aims 1 and 2. A1c will also be measured at all scan visits. Hypoglycemia questionnaires will also be repeated, in addition to repeat cognitive assessments (using different test versions to reduce practice effects).

Note regarding order of visits: As is the case in Aims 1 and 2, CGM placement will occur up to 14 days prior to the subject's first scan of Aim 3 (fMRI or MRS). CGM removal will occur on the same day as the subject's first scan of Aim 3 (fMRI or MRS). Due to the many complexities of scheduling, there is no order that the fMRI and MRS must be performed. The order of scans in no way effects subject safety or research integrity.

Optional Sub Study: Subjects from Aim 1 and 2 with T1DM: (1) hypoglycemia unaware (T1DM-UA) (N=40) and (2) hypoglycemia aware (T1DM-A) (N=25) will be given the opportunity to participate in this optional sub study. We will only contact those previously enrolled participants who agreed to be re-contacted for future research by indicating such on the AIM 1 and 2 consent form.

1. Consenting: Subjects will be consented for this optional Sub study through the Qualtrics study link. The consent form will be provided as a study question. Subject will either click yes or no to agreeing to completed issued questionnaires. If subject, clicks yes and provides name and date, questions from survey will be provided. If subject clicks no, subject will not be provided additional questionnaires.
2. Subject Contact: Only subjects with T1DM and already eligible to participate in Aim 1 and Aim 2 will be contacted via telephone and explained the purpose of the sub-study.
3. Diabetes and health status questionnaires: All participants who agree to participate will be asked to complete questionnaires (all standard, well-validated questionnaires) for assessing hypoglycemia, self-evaluate their diabetes healthcare, general stress and anxiety during the COVID-19 pandemic and unprecedented stay-at-home experience. Questionnaires include:
 - a. Clarke, Gold, Pedersen : Classifies awareness of hypoglycemia, three different measures

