Aim 2 Analysis: Comparisons of glucose levels in specific brain regions will be made using a repeated measures mixed model. Fixed factors include group and glycemic state (e.g. acute hyperglycemia) and their interaction. A random effect for subject will be used to accommodate correlation between repeated assessments. Linear contrasts comparing differences in average brain glucose between groups will be estimated. A significance level of 0.01 will be used to accommodate multiple pairwise comparisons of groups. Similar secondary analyses will be conducted to assess differences in V_{TCA} between groups and fructose production during hyperglycemia. For the rodent studies our preliminary data showed a 1.5 standardized difference in fructose and glutathione concentrations between groups, so a sample size of 14-15 rats per group will provide 80% power to detect a large standardized difference in study outcomes at the two-sided 0.05 significance level. Between-group comparisons, ANOVA and t-tests will be used for continuous variables, where applicable.

Plan for Missing Data: Prevention is the obvious way to control for bias and loss of power from missing data (71). We will follow the intent to treat principle, requiring follow-up of all subjects regardless of treatment³⁴. Postcard and telephone visit reminders will be sent and alternative contacts identified to minimize loss to follow-up. Timely data entry and weekly missing data reports will trigger protocols for obtaining missing data items. Despite these efforts it is reasonable to assume missing data will occur most likely at random³⁵. We will evaluate the plausibility of this assumption using logistic regression to identify factors linked to dropout.

SECTION II: RESEARCH INVOLVING DRUGS, BIOLOGICS, RADIOTRACERS, PLACEBOS AND DEVICES

If this section (or one of its parts, A or B) is not applicable, check off N/A and delete the rest of the section.

A. RADIOTRACERS N/A

B. DRUGS/BIOLOGICS N/A

1. Use of Placebo: Not applicable to this research project

2. Continuation of Drug Therapy After Study Closure Not applicable to this project

B. DEVICES N/A

1. Are there any investigational devices used or investigational procedures performed at Yale-New Haven Hospital (YNHH) (e.g., in the YNHH Operating Room or YNHH Heart and Vascular Center)? Yes No

If Yes, please be aware of the following requirements:

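### Aim 3's 80% power is a two-arm figure, but the procedures describe one group of 40; no Aim 3 analysis is specified, and the 65 to be enrolled does not follow from 40 with 10% dropout

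*Combined protocol and SAP*

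**What the plan says.** **Sample size (item 13, Statistical Considerations).** "The T1DM Unaware group sample size (n=40) was first determined to provide sufficient power for Aim 3". The preliminary brain glucose data compare low- and high-variability groups: "high glucose variability index of 0.455 (SD=0.26"). For change in striatal activity the observed Aware versus Unaware difference is 0.013 (SD 0.016). From these the plan concludes that "for Aim 3 a sample size of 20 T1DM Unaware subjects per arm will provide 80% power to detect a difference of 0.22" (this target is for brain glucose; the one for striatal activity is 0.013). It then adds: "We will enroll 65 Unaware for Aim 3 in order to accommodate a potential 10% dropout rate".

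**Procedures (item 4, Research Plan, Aim 3).** Entry is limited to Unaware subjects who completed Aims 1 and 2, where the Unaware group is 40. Under Group Assignment, "40 T1DM-UA subjects will be assigned to use a Dexcom G6 continuous monitoring system for 8 to 12 weeks", with the end point of use tied to stable glycemic variability. No comparator or allocation is described. On rescanning, "At 12 weeks, all subjects will repeat fMRI and MRS analyses of brain glucose transport/metabolism". The next sentence says almost the same of a subset: "the subjects in Group 2 will repeat fMRI and MRS analyses". Group 2 is defined nowhere.

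**Analysis (item 13).** There are analysis paragraphs for Aim 1 (alpha 0.017) and Aim 2 (alpha 0.01), and none for Aim 3. The only two-sided 0.05 concerns the rodent studies. A general line allows ANOVA and t-tests where applicable.

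**The concern.** Aim 3 is the interventional question, and by the plan's own account its power fixed the Unaware sample size used in all three aims. A power statement has to belong to a test. Here it belongs to a comparison of two arms of 20, while the procedures supply one group measured before and after. With no contrast, alpha or sidedness, and no rule for whether one or both co-primary outcomes must succeed, the Aim 3 test could be settled after the data are seen. The enrolment figure is a separate fault, because 65 Unaware subjects cannot enter an aim that draws on a group of 40.

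**Working it through.** **1. The plan's 80%, taken as a two-arm figure.** Inputs from item 13: 20 per arm; differences 0.22 and 0.013; SDs 0.26 and 0.016. Applying 0.26 to the 0.22 target is inferred from how item 13 leads from one to the other.

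Standardized differences: 0.22/0.26 = 0.846; 0.013/0.016 = 0.8125.

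Two-sample t test, df = 38, noncentrality = d × √(20/2):

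| Alpha (assumed) | Brain glucose | Brain activity |
|---|---|---|
| two-sided 0.05 | 74% | 71% |
| two-sided 0.025 | 64% | 60% |
| one-sided 0.05 | 84% | 81% |

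An unadjusted two-sided 0.05 test needs 23 and 25 per arm for 80%. Baseline adjustment (variance multiplied by 1 − ρ², df = 37) reaches 80% with 20 per arm if the pre-post correlation ρ is at least about 0.37 and 0.45. So 80% can be reached, but only with a choice that the plan does not state.

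**2. The design as described.** With one group, the natural test is follow-up minus baseline. Its power depends on the SD of the within-subject change, which the documents do not give; both quoted SDs come from between-group comparisons. What can be stated is the standardized change detectable with 80% power in a one-sample t test:

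| Completers | two-sided 0.05 | two-sided 0.025 |
|---|---|---|
| 36 | 0.48 SD of change | 0.53 |
| 40 | 0.45 | 0.50 |

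Illustration only, taking the quoted SDs as per-visit SDs with zero pre-post correlation: the SD of change is 0.26 × √2 = 0.368 and 0.016 × √2 = 0.0226. The standardized changes are then 0.22/0.368 = 0.60 and 0.013/0.0226 = 0.57. With 36 completers at two-sided 0.05, power is 94% and 92%. At half those changes it is 42% and 39%.

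**3. Enrolment.** 40/(1 − 0.10) = 44.4, so 45 enrolled for 40 completers. If 40 are enrolled, 40 × 0.90 = 36 complete. Enrolling 65 would leave 65 × 0.90 = 58.5, about 58.

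**4. Totals side by side.**

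- Item 6 (Subject Population): 65 subjects with T1DM (in item 4, 40 Unaware + 25 Aware) plus 25 controls = 90.
- Item 13: 65 Unaware for Aim 3, plus 27 Aware and 27 controls = 119.
- Section III, item 1 (Targeted Enrollment): 150.
- Section III, item 3 (message to potential participants): about 65 for the study.

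**5. Follow-up time.** Group Assignment gives 8 to 12 weeks of device use; the repeat scans are set at 12 weeks. A follow-up-minus-baseline contrast has no single defined time until these are reconciled.

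**The case against.** The strongest reply is that the study is plainly single-arm and the rest is leftover text. Much of this stands. Entry, assignment and the first rescanning sentence all describe one group; Section VI lists one Aim 3 payment schedule; no randomisation or control condition appears anywhere; and the Group 2 sentence nearly duplicates the one before it. A reader might infer that the documents leave two designs evenly balanced, and might cite the missing-data plan: "We will follow the intent to treat principle, requiring follow-up of all subjects regardless of treatment". That wording does not show two arms, since it equally fits a single group in which people who stop using the CGM are still followed. But if the study is single-arm, the sample-size statement belongs to another design, and the analysis for the actual one has not been written.

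A second reply is that no loss of power is shown. That is correct. A reader might infer from 74% and 71% that Aim 3 is underpowered, or that the 80% is a proven arithmetic error. The documents support neither: a one-sided 0.05 test gives at least 80% on both outcomes, and the single-group illustration at the quoted differences exceeds 90%.

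A third reply is that item 13 does name both co-primary outcomes and their target differences, and has a general line on ANOVA and t-tests. This narrows the gap but supplies no Aim 3 contrast, alpha, sidedness or multiplicity rule.

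Finally, 65 may be a mix-up with the total T1DM sample. That is plausible, and it still needs correcting.

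**Conclusion.** The point holds and needs correction. The 80% is a two-arm figure attached to procedures that describe one group of 40, and Aim 3 has no specified analysis. As a two-arm figure it is 74% and 71% at two-sided 0.05 with the quoted SDs, and it reaches 80% on both outcomes only under an unstated choice. Single-arm power cannot be fixed from the documents, because no SD of change is given. The 65 is wrong against the plan's own inputs (45), whatever is assumed about the design.

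The weight rests on the mismatched design text, the missing analysis and the enrolment error, not on a demonstrated shortfall in power. That the single-arm reading is the intended one is an inference from the operative text, though a strong one.

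**What to change.** Reconcile the Aim 3 procedures in item 4 with item 13 so that they describe one design.

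- **If single-arm, as the operative text suggests:** delete the per-arm and Group 2 text. Add an Aim 3 analysis paragraph with a follow-up-minus-baseline contrast in the Unaware group, its sidedness, and alpha for the two co-primary outcomes (0.025 each if either suffices, 0.05 each if both are required). Replace the 80% with the detectable standardized change from the working, noting that no SD of change is available. Limit the conclusion to change after the CGM programme, since without a comparator the effect of time and regression to the mean cannot be separated from it.
- **If two-arm:** define the comparator and allocation in item 4, and restate power with its alpha, sidedness and analysis, including any assumed correlation.
- **In either case:** correct the 65; say whether 40 means enrolled (36 completers) or completers (45 enrolled); align the totals in items 6 and 13 and in Section III, items 1 and 3; and reconcile the 8-to-12-week and 12-week statements so that the follow-up time is defined.

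Cost: for the single-arm route, protocol wording and a more modest Aim 3 claim, with no added subjects if 40 means enrolled and five more Unaware subjects if it means completers. The two-arm route needs a comparator and an allocation procedure, and an unadjusted two-sided 0.05 test would need 2 × 23 = 46 completers for brain glucose or 2 × 25 = 50 for brain activity.
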